- One of the great challenges in developing flavopiridol and applying it clinically has been determining its optimal dosing schedule. Following several different dosing schedules, one strategy that has been very promising in CLL is the application of so-called hybrid schedules of the drug (an infusion for an intermediate time following a bolus dose).

Objectives:

- Assess the toxicity and safety of administration of this hybrid schedule
- Assess the response rate of the hybrid schedule of flavopiridol in relapsed MCL and DLBCL

Eligibility:

- Relapsed MCL or DLBCL
- ECOG P.S. ≤ 2
- Age ≥ 18 years
- HIV serology negative

Design:

- Phase I/II
- Phase I portion consists of 3-4 dose levels of 3-6 patients each
- Administer weekly X 4 and then 2 weeks off (1 cycle). Restage after every 2 cycles. Continue if CR, PR or SD for up to 6 cycles. Dose reductions for toxicity will be addressed in the protocol.
- Phase II portion of the study will be a Simon optimal two-stage design: designed to rule out 20% response rate ($p_0=0.20$) in favor of a 45% response rate ($p_1=0.45$)
- The maximum sample size to be accrued for this study will be 71 patients.

TABLE OF CONTENTS

PRÉCIS	3
TABLE OF CONTENTS	4
1 INTRODUCTION	6
1.1 Study Objectives	6
1.2 Background and Rationale	6
2 ELIGIBILITY ASSESSMENT AND ENROLLMENT	11
2.1 Eligibility Criteria	11
2.2 Research Eligibility Evaluation	11
2.3 Patient Registration	12
3 STUDY IMPLEMENTATION	12
3.1 Study Design:	12
3.2 Drug Administration	13
3.3 Treatment Modifications:	15
3.4 Study Calendar	19
3.5 Off Study Criteria	21
3.6 Post Treatment Evaluation	21
4 SUPPORTIVE CARE	21
4.1 Tumor Lysis Syndrome	21
4.2 Anti-emesis	22
4.3 Neutropenia	22
5 DATA COLLECTION AND EVALUATION	22
5.1 Data collection	22
5.2 Data reporting	22
5.3 Response criteria	22
5.4 Toxicity Criteria	23
6 STATISTICAL CONSIDERATIONS	23
6.1 Data, Safety and Monitoring Board	24
7 HUMAN SUBJECTS PROTECTIONS	24
7.1 Rationale for subject selection	24
7.2 Evaluation of benefits and risks/discomforts	25
7.3 Risk/Benefit Analysis	25

7.4	Consent and assent	25
8	SAFETY REPORTING REQUIREMENTS/DATA AND SAFETY MONITORING PLAN	
	25	
8.1	Definitions.....	25
8.2	NCI-IRB and Clinical Director Reporting	25
8.3	CTEP Adverse Event Reporting Requirements	26
8.4	The Comprehensive Adverse Event and Potential Risks list (CAEPR).....	26
8.5	Adverse Event Characteristics	29
8.6	Expedited Adverse Event Reporting.....	29
8.7	Routine Adverse Event Reporting.....	31
8.8	Secondary AML/MDS	31

1 INTRODUCTION

1.1 STUDY OBJECTIVES

1.1.1 Primary

- Assess the response rate of flavopiridol in patients with relapsed mantle cell lymphoma (MCL) and diffuse large B-cell lymphoma (DLBCL) when administered as a 30 minute loading dose followed by a 4-hour infusion once weekly for 4 consecutive weeks every 6 weeks
- Assess the toxicity profile, dose-limiting toxicity and maximum tolerated dose of flavopiridol administered in the hybrid schedule of a 30 minute loading dose followed by a 4-hour infusion once weekly for 4 consecutive weeks every 6 weeks in patients with relapsed MCL and DLBCL.

[figure not shown]
1.1.2 Secondary

- Determine the pharmacokinetics of flavopiridol when administered by hybrid schedules, correlating this with toxicity and Tumor Lysis Syndrome (TLS).
- Assess tissue from tumor biopsies (where possible before and after flavopiridol) by microarray and protein analysis.

1.2 BACKGROUND AND RATIONALE

1.2.1 Flavopiridol Background

Flavopiridol is a synthetic flavone compound with a novel structure, compared to polyhydroxylated flavones such as quercetin and genistein.

Flavopiridol is obtained from a synthetic process, but its chemical structure is identical to a product obtained from an indigenous plant in India called *Dysoxylum binectariferum*. When flavopiridol was first discovered, it was considered to be a tyrosine kinase antagonist but subsequently, it was shown to reversibly inhibit growth via inhibition of cyclin-dependent kinase (CDK)1 and CDK2[1, 2]. Flavopiridol induced cell cycle inhibition by altering phosphorylation of tyrosine residues as well as antagonizing CDK1 and CDK2 activity as a result of competitive inhibition with ATP[3]. Based on these initial observations, investigators hypothesized that flavopiridol would be effective in rapidly dividing tumor systems where a minimum volume of tumor exists. We now know that flavopiridol has a number of additional targets that include the cyclin D-1 complex over-expressed in mantle cell lymphoma and cyclin H. In addition, studies in lymphoma cell lines have demonstrated activity against activated B-cell (ABC) type cell lines and NF-kappa B down-regulation[4, 5].

1.2.2 Dose Scheduling of Flavopiridol

One of the great challenges in developing flavopiridol and applying it in clinical trials has been its dose scheduling. Initial in vitro work performed at the NCI evaluated a long continuous infusion administration (72 hours: 50 mg/m²/day every 2 weeks)[6]. 72 hours exposure resulted in growth inhibition with little cell recovery over the next 3 days. These experiments provided support for a 72 hour infusion schedule that was subsequently utilized in later phase I studies. Although patients achieved steady state concentrations that had been shown to be cytotoxic in vitro, the response rate in solid tumor and lymphoma patients in the initial Phase I studies was disappointing. This is likely explained by the fact that the effects of flavopiridol are far more potent in fetal calf serum (used for most in vitro experiments) than in human plasma because of high protein binding in human (95-98%) compared to bovine (0%) serum. thus, much higher concentrations appear to be needed *in vivo* to achieve adequate free drug levels.

Following this realization, alternative schedules of administration were investigated. In leukemia and lymphoma models, bolus schedules that achieved high concentrations resulted in potent anti-tumor effects. A marked *in vivo* dose response curve with bolus administration of flavopiridol, compared to 72 hour continuous exposure was observed by Sausville and colleagues[7]. Trials in mantle cell lymphoma and CLL demonstrated that daily bolus schedules induced partial responses compared to long continuous infusions[8-10]. However, the half-life of flavopiridol is short following 1-hour administrations (3-4 hours) and brief exposure to this high concentration is probably inadequate to inhibit cellular targets. One strategy that could potentially produce high concentrations of drug for a relatively prolonged period of time is an infusion of flavopiridol for an intermediate time following a bolus loading dose.

1.2.4 Pharmacokinetics of Flavopiridol

[figure not shown]
As discussed above, the high plasma protein binding of flavopiridol explains its very low free concentration in human plasma compared to media containing fetal calf serum and explains the lack of clinical responses with various schedules. Studies that have assessed the pharmacokinetics of flavopiridol have shown a very wide variability in clearance and volume of distribution due to plasma protein binding.

The elimination half-life of flavopiridol varies based on the infusion duration:

- a) 72 hour infusion: 10-27 hours[11] [14, 15]
- b) 24 hour infusion : 22 hours[16]
- c) 1 hour infusion: 3.5 to 5 hours[11]

The total body clearance ranges from 11-16 L/hr/m

Simulations of the plasma-concentration time curves at the proposed dose-schedules (courtesy of [name]):

We plan to assess and investigate the pharmacokinetics of flavopiridol in this study. We will collect samples at 0.5 , 4.5 and 6 hours following the start of the bolus dose of flavopiridol on doses 1 and 2 of cycle 1. These time-points are based on results from Byrd and colleagues who investigated this hybrid schedule of flavopiridol in patients with CLL.[17]

1.2.5 Rationale for Flavopiridol in MCL and DLBCL

1.2.5.1 MCL

Mantle cell lymphoma (MCL) is an aggressive non-Hodgkin lymphoma (NHL) and constitutes approximately 5-8 % of all NHLs. It usually presents with advanced stage disease, has a median age at diagnosis of approximately 65 years and is considered incurable with chemotherapy and antibody treatment. MCL is characterized by a distinct biologic profile and pathogenesis. The t(11;14) chromosomal translocation and over-expression of the cell cycle regulatory protein cyclin D1 are characteristic molecular findings. Recent advances have identified distinct intracellular pathways that likely play an important role in the pathobiology of MCL. This elucidation has led to the testing of agents that specifically target abnormal pathways in MCL cells. One of the most attractive therapeutic targets for MCL is the cyclin D1 complex which is associated with cell cycle deregulation. Flavopiridol targets a number of different cellular pathways and processes. It induces cell cycle arrest by cyclin dependent kinase (cdk) inhibition and its actions include the inhibition of cdk7 and cyclin H, and the down-regulation of cyclin D1 and D3 expression leading to G1 arrest. Exposure of mantle cell lymphoma cell lines to flavopiridol-induced apoptosis has been associated with decreased levels of cyclin D1 expression. Therefore, investigating flavopiridol in patients with MCL is a very interesting strategy. In MCL, flavopiridol at a dose of 50 mg/m²/day has been tested both as a 72 hour continuous infusion every 2 weeks and as a 1 hour infusion daily X 3, every 3 weeks[9, 10]. No patients (0/10) responded to the continuous infusion schedule but 3 of 27 patients had a partial response to the bolus schedule (12% PR) – there is no statistical

difference between these two portions (Fisher's exact test, $p=0.55$). These results suggest that the continuous infusion schedule achieved inadequate steady state levels of drug to induce cytotoxicity and that the bolus schedule probably induced adequate drug levels but for too short a time to achieve significant tumor kill. Thus, our hope is that the hybrid schedule of flavopiridol will achieve high enough and adequate cytotoxic drug levels (bolus) that are maintained for enough time (infusion) to effectively kill tumor cells.

1.2.5.2 DLBCL

DLBCL is also an aggressive disease and the most common subtype of NHL. Gene expression profiling has revealed that there are at least 3 distinct sub-types of DLBCL and one of these, the activated B-cell like (ABC) type, is associated with a worse prognosis and patients who relapse after initial therapy are more likely to have this type. It is particularly worthwhile investigating and developing therapies that can target the ABC type. Studies of flavopiridol lymphoma cell lines have demonstrated strong activity of flavopiridol on OCI-Ly3 lymphoma cell lines which are an excellent model of the ABC type of DLBCL[4]. Flavopiridol inhibits the NF-kappa B pathway which is constitutively activated in the ABC type of DLBCL. Thus, the ABC type of DLBCL may be a particularly attractive target for flavopiridol and therefore our interest in investigating the drug in DLBCL[5].

1.2.5.3 Hybrid schedule in MCL and DLBCL

We propose to evaluate the safety of the hybrid schedule of flavopiridol which is administered as a 30 minute bolus followed by a 4 hour infusion weekly x 4 consecutive weeks, followed by 2 weeks without flavopiridol treatment for a cycle duration of 6 weeks in patients with relapsed or refractory MCL and DLBCL. To determine the safe tolerated dose of the hybrid schedule, a phase I dose escalation will be performed to determine the MTD. To determine the efficacy of the hybrid schedule at the MTD, a phase II study will be performed in MCL and DLBCL.

There are distinct molecular targets amenable to flavopiridol in both MCL and DLBCL, which we plan to evaluate. Among these are the cyclin D-1 complex, NF-kappa B, various cyclin dependent kinases and various specific genes. The rationale for studying these markers is as follows: In mantle cell lymphoma cells, we wish to investigate if markers such as cyclin D-1 and certain cyclin dependent kinases are down-regulated by flavopiridol and if there are any patterns of association between levels of certain markers and outcome. In DLBCL, we will assess in an exploratory manner if flavopiridol is more effective in the ABC versus GCB subtype of DLBCL. Because these studies are exploratory and hypothesis generating, the study will not be powered to answer a specific biological question.

Given the activity of flavopiridol when administered as a bolus schedule, we are interested in investigating the hybrid schedule of Byrd and colleagues that has yielded very promising results in CLL/SLL. We aim to both assess the efficacy of the hybrid schedule in MCL and DLBCL and in addition determine if tumor lysis syndrome, which has been reported in approximately 15% of CLL/SLL patients treated with this schedule, occurs in MCL and DLBCL patients.

2 ELIGIBILITY ASSESSMENT AND ENROLLMENT

2.1 ELIGIBILITY CRITERIA

- 2.1.1 Previously treated mantle cell lymphoma or diffuse large B-cell lymphoma (to include mediastinal (thymic) large B-cell lymphoma; transformed large B-cell lymphoma; follicular grade IIIB large B-cell lymphoma; intravascular large B-cell lymphoma)
- 2.1.2 Confirmed pathological diagnosis at the National Cancer Institute, NIH.
- 2.1.3 Recurrent measurable disease (measurable disease in 2 dimensions or leukemic disease which can be quantified and followed)
- 2.1.4 Prior anthracycline-based treatment for patients with DLBCL
- 2.1.5 Age > 18years
- 2.1.6 ECOG performance 2 or better
- 2.1.7 Major organ function: ANC > 1000/mcL, Platelet > 50,000/mcL, Creatinine < 1.5 mg/dL or creatinine clearance > 60 mL/min; SGPT < 5 x upper limit of normal; bilirubin < 2 mg/dL (total) except < 5 mg/dL in patients with Gilbert's syndrome as defined by > 80% unconjugated. ANC and platelet requirements must be met independent of transfusion.
- 2.1.8 Informed consent and willingness to use contraception by both men and women.
- 2.1.9 Both male and female patients must be willing to use adequate contraception (to include effective barrier methods of contraception) or to completely abstain from heterosexual intercourse while on protocol treatment.
- 2.1.10 Not pregnant or nursing because of an unknown potential for teratogenic or abortifacient effects
- 2.1.11 HIV serology negative. HIV positive patients receiving combination anti-retroviral therapy are excluded from the study because of possible pharmacokinetic interactions with flavopiridol. Additionally, the biology of HIV associated DLBCL's is often quite different from HIV negative disease due to involvement of EBV.
- 2.1.12 Hepatitis B surface antigen negative.
- 2.1.13 No active CNS lymphoma. These patients have a poor prognosis and because they frequently develop progressive neurological dysfunction that would confound the evaluation of neurological and other adverse events.
- 2.1.14 No history of inflammatory bowel disease unless this has been inactive for a period of 2 or more years.
- 2.1.15 Recovery from toxicity of prior therapy to a grade 1 or less.
- 2.1.16 No systemic cytotoxic or experimental treatments within 4 weeks of treatment.
- 2.1.17 No WBC > 100,000 cells/mcL

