2.2 RESEARCH ELIGIBILITY EVALUATION

Blood tests (except serologies) and pregnancy test to be done within one week of study entry, other studies to be done within 4 weeks before study entry:

- Complete History and Physical examination.
- CBC, differential, PT, PTT, SGOT, SGPT, LDH, alkaline phosphatase, bilirubin, albumin, calcium, phosphate, uric acid, creatinine (24 hour creatinine clearance if serum creatinine > 1.5 mg/dL), electrolytes, urinalysis, HIV serology, hepatitis B surface antigen and Anti Hepatitis B core antibody.
- Unilateral bone marrow aspirate and biopsy if not performed within 1 month.
- HCG (urine) in women of childbearing potential.
- Electrocardiogram.
- Staging: CT scans of chest, abdomen and pelvis.
- PET as clinically indicated.
- Head CT or Brain MRI and lumbar puncture with flow and cytology as clinically indicated.

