3.4 STUDY CALENDAR

Studies	Pre-therapy^A	Day -1 or day 1 of each cycle	Weekly during therapy	Every second cycle	Follow-up^B
Hx; PE; VS; PS	x	x			x
Tumor Measurement	x			x	x
CBC/diff	x ^F	x	x		x
Electrolytes, Creatinine/BUN ALT, AST, Bilirubin, LDH, Ca ⁺⁺ , Phos, Mg	x ^F	x	x		x
10 mL red top for serum storage	x	x			x
Clinical PET scan ^D	x				
CT chest/abdomen/pelvis ^C	x			x	x
Bone marrow biopsy & aspirate and peripheral blood for flow cytometry where indicated ^E	x			x ^E	
Tumor biopsy, timed blood collections and/or apheresis ^G	x				
Tumor Lysis Syndrome monitoring		x ^H			

- A- Initial assessment may be performed within 4 weeks prior to starting treatment.
- B- Follow-up to occur every 3-4 months until disease progression requiring initiation of non-protocol therapy.
- C- Extent of CT scans may be limited to assess sites of prior disease.
- D- PET scans will be performed pre-therapy if clinically indicated. PET may be obtained at the first post-treatment restaging in patients in CR.
- E- Obtain pre-treatment and after patients achieve CR by other staging.

F- These laboratory tests must be obtained within one week of initial treatment.

G- Where possible, tumor biopsies will be obtained by core needle biopsy or surgery pre-treatment. In select patients a repeat core biopsy of superficial nodes may be carried out within 24 hours from the end of the first flavopiridol infusion. Snap freeze and store tissue biopsies for translational studies at -80°C. Lymphapheresis may be performed pre-treatment in patients with leukemic MCL and may be repeated after the completion of the flavopiridol infusion. Timed blood samples of 20-40 mL each, typically pre-treatment, at 1 hour, 3hours, 6hours and 24hours may be obtained in selected patients during the first flavopiridol infusion. In patients with leukemic disease this may be repeated during the second flavopiridol infusion. Research blood collections will be limited to less than 450 mL in any 6 week period.

H- Please refer to section 4.3.6 on TLS monitoring for details of what is required.

- **Pharmacokinetics:** Collect one 6 mL sodium heparin tube at the following time points on dose 1 and 2 of cycle 1 only: 30 minutes after the start of the bolus infusion, 4.5 hours and 6 hours after the start of the bolus infusion. All PKs should be placed directly on ice and then refrigerated until specimen is picked up.

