5.3 RESPONSE CRITERIA

Response criteria for lymphomas as per Cheson criteria. [18] with modifications as described below. Responses must last for at least 4 weeks off treatment.

- Complete response (CR): Complete disappearance of all detectable clinical and radiographic evidence of disease and disappearance of all disease-related symptoms if present before therapy, and normalization of those biochemical abnormalities (e.g. LDH) definitely assignable to the lymphoma. All lymph nodes must have regressed to normal size (≤ 1.5 cm in greatest diameter if > 1.5 cm before therapy). Previously involved nodes that were 1.1 to 1.5 cm in greatest diameter must have decreased to ≤ 1 cm or by more than 75% in the sum of the products of the greatest diameters (SPD). Spleen, if considered to be enlarged before therapy, must have regressed in size and not be palpable on physical examination. The bone marrow must show no evidence of disease by

histology. Flow cytometric, molecular or cytogenetic studies will not be used to determine response.

- Complete response unconfirmed (CRu): As per CR criteria except that if a residual node is > 1.5 cm, it must have regressed by $> 75\%$ in SPD. Lymphocyte aggregates within the bone marrow must be negative for B-cell markers (e.g. L26).
- Partial response: $\geq 50\%$ decreased in SPD of 6 largest dominant nodes or nodal masses. No increase in size of nodes, liver or spleen and no new sites of disease. Splenic and hepatic nodules must regress by $\geq 50\%$ in the SPD. Bone marrow is irrelevant for determination of a PR.
- Definition of progressive disease (PD): Defined by at least one of the following: $\geq 25\%$ increase in the sum of the products of at least two lymph nodes, appearance of new lymph nodes, $\geq 50\%$ increase in the size of the liver and/or spleen as determined by measurement below the respective costal margin, appearance of new palpable hepatomegaly or splenomegaly that was not previously present, $\geq 50\%$ increase in the absolute number of circulating lymphocytes.
- Definition of stable disease: (SD) will be characterized by not meeting any of the criteria outlined above.

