6 STATISTICAL CONSIDERATIONS

This will be a Phase I/II study.

- The Phase I portion of the study will have three to four treatment dose levels. Three to six patients will be accrued on each of the dose levels. Enrollment will proceed on the next dose level if 0 of 3 or 1 of 6 patients experience DLT. MTD will be defined as the highest dose level in which 0-1/6 patients experience DLT.
- The Phase II portion of the study will use a Simon optimal two-stage design in each of the two histology cohorts, MCL and DLBCL. For each of these two, the trial will be designed to rule out a 20% response rate ($p_0=0.20$) in favor of a 45% response rate ($p_1=0.45$). The justification for this is that other regimens could be associated with a 20% response rate and the objective is to demonstrate if this agent is superior to that level. With $\alpha=\beta=0.10$, the first stage for each histology would accrue 14 patients (28 total for the first stage, but by performing response evaluation on the 6 patients treated at the MTD in the phase I portion of the study and by counting them in each phase II arm according to their histology, this would only require 22 newly enrolled patients in the first stage). If 0-

3 of the 14 in a given arm have a PR or CR, then no further patients would be accrued. If 4 or more of the 14 patients in an arm have a CR or PR, then accrual would proceed to a total of 25 patients in that arm (11 more patients beyond the 14 in the first stage). If 4 to 7 have a PR or CR, then this is insufficient activity to warrant further investigation while 8 or more responses in 25 would be adequate to justify further development. Under the null hypothesis, 20%, the probability of early termination would be 70%.

- With up to 24 patients enrolled in the phase I portion, and 50 - 6 (6 are used for response evaluation from the phase I portion)=44 new patients potentially required for the phase II portion, a total of 24+44=68 total evaluable patients may be required if both arms need to go to the second stage. To allow for a small number of non evaluable patients, the accrual ceiling will be set at 71.
- To determine if patients have responded, they will be assessed every 8 weeks. The latest time for determining a response will be after 16 weeks or 4 cycles of therapy.
- It is expected that up to 3 years may be required to accrue up to 71 total patients permitted to enroll onto this trial.

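### The only timed limit on prior therapy omits radiotherapy and does not clearly cover antibodies or corticosteroids, so their effect can be scored as a flavopiridol response

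*Combined protocol and SAP*

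**What the plan says.** All references are to the combined protocol and SAP.

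- **Section 2.1, criterion 2.1.16:** "No systemic cytotoxic or experimental treatments within 4 weeks of treatment". No other criterion puts a time interval on earlier treatment.
- **Criterion 2.1.15:** "Recovery from toxicity of prior therapy to a grade 1 or less". This concerns side effects, not anti-tumour effect.
- **Criterion 2.1.3:** "Recurrent measurable disease (measurable disease in 2 dimensions or leukemic disease which can be quantified and followed". It has no rule on irradiated lesions and does not require progression since the last therapy.
- **Section 1.2.5.1:** MCL "is considered incurable with chemotherapy and antibody treatment". Antibody treatment is named separately from chemotherapy.
- **Baseline imaging:** section 2.2 sets time limits for blood and pregnancy tests and has "other studies to be done within 4 weeks before study entry", which takes in the staging CT. Footnote A of the study calendar (3.4) says "Initial assessment may be performed within 4 weeks prior to starting treatment".
- **Section 5.3:** a PR needs a fall of at least 50%, "decreased in SPD of 6 largest dominant nodes or nodal masses", with no growth elsewhere and no new sites. A response must hold for at least 4 weeks off treatment.
- **Section 3.5:** starting non-protocol treatment takes a patient off study.
- **Section 6:** each histology arm is a single-arm two-stage design. "If 4 or more of the 14 patients in an arm have a CR or PR", the arm continues to 25 patients, and 8 or more responses count as success. There is no rule for recent other anti-lymphoma therapy.

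**The concern.** Response rate is a primary objective, and neither arm has a comparator. Any shrinkage recorded against baseline is credited to flavopiridol, whatever caused it. A washout rule and a baseline scan taken after the last prior therapy are the usual protections.

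Here the washout is narrow. Radiotherapy to a node is not systemic. A licensed antibody or a corticosteroid course is not experimental, and neither is plainly cytotoxic. The protocol does not define cytotoxic, so investigators may read it differently. The scan window then supplies a route for carry-over: a patient can be scanned, receive one of these treatments, enter the study, and have that treatment's effect measured from the older scan. A delayed effect can be credited in the same way even if the scan came after the treatment.

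At stake is the go/no-go decision in each arm. The boundary leaves little room for extra responders before the false-positive risk passes the planned 10%.

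**Working it through.** **Step 1. Does another section close the gap?**

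| Provision | Why it does not |
|---|---|
| 2.1.15 | Toxicity recovery only |
| 2.1.3 | Recurrent, measurable disease; silent on irradiated lesions and on progression since last therapy |
| 3.5 | Reaches non-protocol treatment started on study, not treatment completed before entry |
| 5.3, 4-week durability | Filters short-lived effects, not durable ones |
| 6 | Counts every CR or PR |

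**Step 2. Reproduce the plan's own figures.** Inputs from section 6: p0 = 0.20, p1 = 0.45, alpha = beta = 0.10, n1 = 14, n = 25; stop at 3 or fewer of 14; success at 8 or more of 25.

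With X1 ~ Bin(14, p) and X2 ~ Bin(11, p):

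- P(early stop) = P(X1 ≤ 3)
- P(success) = Σ over x = 4 to 14 of P(X1 = x) · P(X2 ≥ 8 − x)

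At p = 0.20: early stop 0.698 (the plan states 70%) and success 0.0933, within the planned 0.10. At p = 0.45: success 0.9026. The design is correctly stated, and the point does not dispute it.

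**Step 3. How much slack is there?** At p = 0.203, P(success) is 0.0999. An apparent response rate of about 20.3% therefore uses up the 10% allowance.

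**Step 4. Upward case (scan before the other therapy, or delayed effect).** The documents give no carry-over rate, so both inputs are assumptions: f is the share of patients affected and c is their probability of being scored a responder. With a true flavopiridol rate of 20%, the apparent rate is p = (1 − f) × 0.20 + f × c. Example: f = 0.10, c = 0.6 gives 0.18 + 0.06 = 0.24.

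| f | c | p | P(success) |
|---|---|---|---|
| 0 | – | 0.200 | 0.093 |
| 0.02 | 0.4 | 0.204 | 0.102 |
| 0.02 | 0.6 | 0.208 | 0.112 |
| 0.05 | 0.4 | 0.210 | 0.117 |
| 0.05 | 0.6 | 0.220 | 0.143 |
| 0.10 | 0.4 | 0.220 | 0.143 |
| 0.10 | 0.6 | 0.240 | 0.204 |
| 0.20 | 0.4 | 0.240 | 0.204 |
| 0.20 | 0.6 | 0.280 | 0.355 |

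A lower c is milder: f = 0.05, c = 0.25 gives p = 0.2025 and 0.099, inside the planned 10%.

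In counts: if one stage 1 patient is a certain carried-over responder and the other 24 respond at 20%, P(success) is 0.173.

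**Step 5. Downward case (scan after the other therapy).** Nodes are already reduced at baseline, so a further 50% fall is harder to show, and regrowth may be scored as progression. With f = 0.10 and c = 0.1, p = 0.18 + 0.01 = 0.19 and P(success) is 0.073.

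**The case against.** Several counter-arguments have force.

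- **Direction.** A reader might infer that the bias can only favour the drug. The documents do not support that. They fix how old the baseline scan may be, not whether it precedes or follows the last therapy, and step 5 shows the effect can run the other way.
- **Window.** A reader might infer that such treatment could be started right up to the first dose. Registration follows consent within 24 hours (2.3), and from then starting non-protocol treatment is an off-study criterion (3.5). The open window ends at study entry.
- **Durability.** Restaging comes after 2 cycles of 6 weeks, that is 12 weeks (3.2), or every 8 weeks (section 6), and a response must last 4 weeks off treatment. A brief steroid effect is unlikely to survive that. Durable antibody or radiotherapy effects can.
- **Radiotherapy to one node.** It yields a PR only if that node dominates the summed products, nothing else grows and no new site appears.
- **Recurrent disease.** A patient still responding to an antibody may not meet 2.1.3. The criterion does not, however, require progression since the last therapy.
- **Evidence of frequency.** Section 1.2.5.1 shows that antibody is a recognised MCL treatment. It says nothing about DLBCL, or about antibody use in the weeks before entry.
- **Size.** Both f and c are assumed, and mild values keep the risk within 10%.
- **Timing.** Section 5.2 says the protocol has been completed with CTEP from Amendment J (2015), so a change to eligibility may come too late for most patients.

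These points limit the direction, reach and certainty of the concern. None of them brings radiotherapy, licensed antibodies or corticosteroids under a timed rule.

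**Conclusion.** The gap is real. Criterion 2.1.16 is the sole timed limit on prior therapy. It leaves out local radiotherapy and is unclear on licensed antibodies and corticosteroids. Together with a baseline scan up to 4 weeks old and no lesion or progression requirement, it allows another treatment's effect to count towards the 8 of 25.

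The size is unknown. Against 0.093 for the design as planned, the false-positive risk at a true rate of 20% is 0.10 to 0.35 per arm. That range assumes 2% to 20% of patients are affected in the upward direction and are scored as responders with probability 0.4 to 0.6. If baseline scans mostly follow the other therapy, the risk could fall below 0.093. The documents do not show that any bias occurred, or which direction it would take; they show only that the plan does not prevent it. The sample size and decision rule need no change.

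**What to change.** 1. Reword 2.1.16 to cover all prior anti-lymphoma therapy, naming antibodies, corticosteroids given for lymphoma, and radiotherapy. The interval for each is a clinical choice for the sponsor; the documents give no basis for carrying the existing 4 weeks over to steroids or radiotherapy.
2. Require in 2.2 and footnote A of 3.4 that the baseline tumour measurement follow the last prior anti-lymphoma therapy.
3. Add to 2.1.3 that at least one measurable lesion is unirradiated or has progressed since radiation.
4. For patients already enrolled, list each responder's last prior therapy and its date, with the baseline scan date beside it. Report the response rate for each arm a second time with affected responders counted as non-responders.

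Items 1 to 3 are wording changes and leave the 14/25 design as it is. A few patients would wait, need a repeat baseline scan, or not be enrolled. Item 4 needs only treatment-history and scan dates.
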